Nevertheless, analysis of baseline data from Study 1 has identified strong associations between higher SAF and malnutrition whereas no correlations were observed between higher SAF and high dietary AGE intake. Correction of malnutrition may therefore represent a more important dietary intervention to reduce accumulation of AGE in people receiving dialysis. We further reasoned that placing people with malnutrition on a restrictive diet may worsen their malnutrition and we have therefore adapted our original research plan to include an observational study to assess the impact of correcting malnutrition on SAF by providing a dietitian supervised nutritional support intervention, which essentially involves the usual/standard dietetic care/advice provided by the NHS with some additional supervision, follow-up and approved dietary supplements (also provided by the NHS), rather than a randomised trial of dietary AGE restriction.

The results from the present project will benefit people on dialysis because they may demonstrate that the correction of malnutrition decreases the SAF levels in this population. Published observational studies suggest that reduction of SAF levels will in turn be associated with a reduction in the high morbidity and mortality rates associated with chronic dialysis and, consequently, healthcare costs. Improved survival and reduced comorbidity would also be expected to improve the quality of life of people on dialysis.

TRIAL / STUDY OBJECTIVES AND PURPOSE

PURPOSE

The purpose of the present project is to investigate the association between AGE accumulation and adverse outcomes (mainly mortality) and the impact of a dietary intervention on SAF levels in people on HD and PD.

PRIMARY OBJECTIVES

Study 1:

- To investigate whether the SAF levels increase over time in prevalent and incident HD and PD participants.
- To investigate one-year survival in relation to increased SAF levels.

Study 2:

- To investigate whether the correction of malnutrition by an intensive nutritional intervention results in a decrease in SAF levels in people on PD and HD.

SECONDARY OBJECTIVES

Study 1:

- To determine the most important factors associated with change in SAF over time.
- To investigate the association of increased SAF levels with morbidity, health-related quality of life and nutritional status.
- To investigate the association between SAF levels and changes in visual function.

Study 2:

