- To investigate the effect of an intensive nutritional intervention on the improvement of health-related quality of life and nutritional markers.

DETAILS OF DEVICE(S)

No products will be used in the present project.

Description

The medical device that will be used in the present project is a validated "AGE reader Standard Unit (SU)". The AGE reader is a medical device used in clinical research which can non-invasively measure tissue accumulation of AGE through a fluorescent technique called SAF.

The AGE reader SU illuminates a skin surface of 1 cm², guarded against surrounding light, with an excitation light source between 300 and 420 nm (peak excitation ≈370 nm). Light from the skin is measured with a spectrometer (AVS-USB2000, Avantes Inc., Eerbeek, The Netherlands) in the 300-600 nm range, using a 200-µm glass fibre. SAF will be measured as the ratio between emission and excitation, calculated in arbitrary units (AU), by dividing the intensity of the fluorescent light coming from the skin (measured as area under the curve [AUC] of fluorescent wave lengths between 420 and 600 nm) by the intensity of the emitted light (measured as AUC of wave lengths between 300 and 420 nm) multiplied by 100. For each participant, three measurements will be performed on the volar surface of the lower arm at ≈10 cm below the elbow, ensuring that the area has normal skin without visible vessels, scars or other abnormalities. For HD participants, only the non-fistula arm will be used and evaluations will take place prior to dialysis sessions (Siriopol et al., 2015). This technique is non-invasive and there is no risk of harm to the participant. Measurements take only a few minutes.

The AGE reader SU will be used by [name] (PhD student) following user instructions provided by the manufacturer.

Manufacture

The name of the manufacturer is DiagnOptics Technologies BV ([name])

The AGE reader SU is a distributed CE marked product covered by the "CE Marking of Conformity Certificate", reference number: 2085393CE01, delivered by DEKRA Certification B.V., Arnhem, The Netherlands, Notified Body Identification Number 0344, and conforms to the required technical documentation, in accordance with Annex VII of the "EC-Directive", the Council Directive 93/42/EEC of 14 June 1993, concerning medical devices.

The AGE reader SU will be used in the present project in accordance with this CE marking.

Packaging and labelling

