- There will not be any safety endpoints for these studies.

Stopping rules and discontinuation

Participant Withdrawal

Participants will be withdrawn from the study if they withdraw their consent at any time. Participants may be withdrawn from the study at the discretion of the Investigator. Participants will be made aware that withdrawal will not affect their future care. Participants who withdraw will be asked for permission to retain data already collected for use in the final analysis.

If participants fail to attend for their study visits, a member of the research team will try to contact them by telephone within 24 hours of their appointment and by written correspondence within a week of the missed appointment. Multiple attempts at contact will be made by the research team over a period of a month before stating that a participant has been lost to follow-up.

Participants will be withdrawn from the study if they:

- Withdraw their consent at any point.
- Become pregnant.
- Decline to comply with the dietetic intervention (Study 2 only).

Criteria for terminating the study

Study 1 is observational and will therefore only be terminated if it becomes clear that for unforeseen reasons the study is not feasible.

The intervention in Study 2 is not expected to be associated with any adverse effects. Study 2 will therefore only be terminated if it becomes clear that for unforeseen reasons the study is not feasible.

RANDOMIZATION AND BLINDING

Maintenance of randomization codes and procedures for breaking code

TRIAL/STUDY MANAGEMENT

The Chief Investigator (CI; [name]) has overall responsibility for the study and shall oversee all study management. The data custodian will be the CI.

The study will be coordinated from the University of Nottingham campus at the Royal Derby Hospital. Data will be collected at the Renal Unit of the Department of Nephrology at the Royal Derby Hospital (Derby Teaching Hospitals NHS Foundation Trust) and stored at the University of Nottingham.

[name] (PhD student), [name] and [name] are responsible for study planning, recruitment, consenting, data collection, handling and interpretation.

DURATION OF THE TRIAL / STUDY AND PARTICIPANT INVOLVEMENT

Study Duration:

Study 1:

Participant recruitment will begin on June 2016 with an anticipated recruitment period of 14 months. Therefore, all baseline data and measurements will be collected and performed between June 2016 and August 2017.

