Routine blood/laboratory tests will be performed at baseline and monthly and will include haemoglobin, HbA1C, urea, creatinine, potassium, phosphate, calcium, sodium, albumin, total proteins, cholesterol, triglycerides and intact parathyroid hormone. Pre- and post-dialysis blood samples (10 mL) will be taken at baseline, 3, 6, 9 and 12 months of follow-up and centrifuged to obtain at least 2 mL of serum and 2 mL of plasma which will be frozen and stored at -80°C for subsequent analysis of circulating AGE levels (CML and pentosidine) and markers of inflammation (TNF- α , IL-6, CRP and others).

Nutritional assessments will be performed at baseline and at 6 and 12 months of follow-up and will include: three 24-h dietary recalls to assess energy, fat and protein intake, a validated food frequency questionnaire to evaluate dietary AGE intake; the 7-point scale SGA for the classification of the nutritional status (normal, mild-moderate malnutrition and severe malnutrition) and anthropometric measurements and indexes (weight, height, mid-arm circumference, triceps skinfold thickness, body mass index, hand-grip strength and mid-arm muscle area).

Participants will have all aspects of their visual acuity assessed at baseline and 12 months. Those on HD will be tested before and after a single mid-week dialysis session. Participants will initially be asked a screening questionnaire to assess whether or not they note a change in their visual acuity or experience visual disturbances peri dialysis. The assessments will include near, distance, contrast and colour vision assessed using the Jaeger near vision chart, standardized Early Treatment Diabetic Retinopathy Study (EDTRS) testing, Pelli-Robson Contrast Sensitivity Chart, and Ishihara Color Vision Test, respectively. Participants will be asked to bring their glasses or wear their contact lenses on the study day to assess best corrected visual acuity.

Health-related quality of life will be evaluated at baseline and at 6 and 12 months of follow-up with the 36-Item Short Form Health Survey (SF-36) and EQ5D questionnaire.

After the first year of the study, SAF readings and questionnaires will be repeated once a year for up to five years.

Study 2 - Observational non-randomised proof of principle study

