The Study 1 (prospective/longitudinal) involves SAF measurements and visual function, nutritional and quality of life assessments during one year of follow-up. Therefore, there is no need for an assessment of participant compliance with the study protocol. Should the participant not complete the study day, this will be classified as a withdrawal rather than non-compliance (see Section **Participant Withdrawal**).

Compliance with the intervention of Study 2 will be evaluated by means of three 24-h dietary recalls every month (1 dialysis day, 1 non-dialysis day and 1 weekend day for the HD participants and 2 weekdays and 1 weekend day for the PD participants).

Criteria for terminating trial

Study 1 is observational and will therefore only be terminated if it becomes clear that for unforeseen reasons the study is not feasible.

The intervention in Study 2 is not expected to be associated with any adverse effects. Study 2 will therefore only be terminated if it becomes clear that for unforeseen reasons the study is not feasible.

TRANSPORT AND STORAGE OF THE TISSUES

Blood samples (10 mL) will be collected at intervals as described and centrifuged. At least 2 mL of serum and 2 mL of plasma will be stored at -80°C for future analysis.

Samples and data will be stored in a linked anonymised format. Samples will be labelled using a combination of study reference, unique study identifier and cross referenced with location code numbers to permit accurate linkage to study data and the consent form.

The master database will be held by the CI in a password encrypted file.

Where participants do not agree to the future use of the samples, they will be destroyed in accordance with the Human Tissue Act, 2004.

LABORATORY ANALYSES

Routine blood/laboratory tests will be analysed in a local NHS laboratory at the Royal Derby Hospital, which is serviced and managed according to national standards and governance frameworks. No DNA or RNA extraction will occur as part of this study. Assays for CML and inflammatory markers will be conducted in research laboratories at the University of Nottingham.

STATISTICS

Methods

Statistical analysis will be conducted by [name] (PhD student), [name] and [name]. Data management and statistical analyses will be performed using statistical software SPSS version 22.0.

Data will be presented as mean \pm standard deviation, median (percentiles 25%-75%), or percentages, as appropriate.

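### No rater, order or masking is set for SGA relative to SAF, so SAF-SGA associations at remaining visits could be inflated; fixing the order is nearly free

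*Combined protocol and SAP*

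**What the plan says.** **People.** TRIAL/STUDY MANAGEMENT names three people, including the PhD student, who "are responsible for study planning, recruitment, consenting, data collection, handling and interpretation". The Description under DETAILS OF DEVICE(S) assigns the AGE reader to one operator: "PhD student) following user instructions provided by the manufacturer". The Statistics section (Methods) also lists the PhD student and two others: "Statistical analysis will be conducted by".

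**Assessments.** For Study 1, "Nutritional assessments will be performed at baseline and at 6 and 12 months of follow-up and will include" "the 7-point scale SGA for the classification of the nutritional status". The verb is passive and no rater is named. SAF is read at the same three time points, and also at 3 and 9 months. In Study 2, SAF and SGA coincide at baseline and month 6, and again no SGA rater is named. The vision examiner is not named either; of haemodialysis (HD) participants the plan says "Those on HD will be tested before and after a single mid-week dialysis session".

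**Order and masking.** Neither assessment section sets an order or restricts access to SAF values. The synopsis row on randomization and blinding deals with randomization only.

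**Use of the scores.** The secondary endpoints in the Trial Design section include the association of SAF with nutritional status, SGA included, in both studies. Study 2 entry requires an SGA of 1 to 5.

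**Expectation.** The background section reports that "analysis of baseline data from Study 1 has identified strong associations between higher SAF and malnutrition", and gives this as the reason for adopting Study 2.

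**The concern.** The background section describes SAF as operator independent, so the side of the association that is open to influence is the judged score. Followed as written, the plan allows an SGA to be given by someone who has just read the participant's SAF, or remembers it, and who works in a team that already expects high SAF to go with poor nutrition. A small, unintended lean in borderline ratings would push the SAF-SGA association away from zero. Once the scores are recorded, the planned correlations and regressions cannot separate that lean from a real relationship within the SGA data. What is at stake is the credibility of the SGA-based secondary results from here on.

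**Working it through.** **Which visits are still open.** This version is dated 4 October 2017. Study 1 baseline was planned for June 2016 to August 2017, so it should be complete. Adding 6 and 12 months puts the month-6 visits between December 2016 and February 2018 and the month-12 visits between June 2017 and August 2018. Some of the former and most of the latter are still to come. Study 2 starts in December 2017, so all of its SGA scores are still to come.

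**Inputs from the plan.** Study 1 has 100 HD + 40 peritoneal dialysis = 140 prevalent participants, and up to 140 + 30 = 170 with the incident group. The significance rule is p ≤ 0.05. The plan gives no coefficient, p-value or sample size for the SAF-malnutrition association, so there is no stated figure to reproduce.

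**How small a correlation is significant.** |r| = t / √(n − 2 + t²). At n = 140, t = 1.977 and |r| = 1.977 / √(138 + 3.91) = 0.166. At n = 170, |r| = 0.151.

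**Effect of one-point shifts (illustration).** Assumptions: no true association; SGA is a rounded normal with mean 5.3 and SD 1, limited to 1-7; Spearman test; 4,000 simulated studies per scenario.

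Two-way shift: in a share f of all participants, SGA moves down one point if SAF is above the median and up one point if below.

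| f | p ≤ 0.05, n = 140 | p ≤ 0.05, n = 170 | mean rho (n = 140), about |
|---|---|---|---|
| 0 | 5% | 5% | 0 |
| 10% | 15% | 17% | −0.08 |
| 20% | 40% | 47% | −0.14 |
| 30% | 73% | 81% | −0.21 |

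One-way shift: SGA is lowered one point in 10%, 20% or 30% of the high-SAF half only. At n = 140 the rejection rate is about 7%, 15% and 27%, with mean rho about −0.04, −0.08 and −0.11. With other assumed SGA distributions (25% or 35% of participants scoring 5 or below) the rates are 6-7%, 12-15% and 22-28%.

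**What a strong association would need.** If the rater shifts SGA by b SD per SD of SAF, the induced correlation is r = b / √(1 + b²). For b = 0.2, r = 0.2 / √1.04 = 0.20. For b = 0.6, r = 0.6 / √1.36 = 0.51. If strong means r near 0.5 (an assumption), a shift of about 0.6 SD per SD is required. Lowering SGA one point in half of the high-SAF group gives only about 0.16 to 0.19.

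**Can an order be applied as the plan stands?** The device description places SAF in HD participants before the dialysis session. The Study 1 procedures place it within the first hour of treatment. The two statements conflict, and the sequence on the day depends on which one applies.

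**The case against.** A reader might infer that rater knowledge produced the association on which Study 2 rests. The documents do not support this. That association comes from Study 1 baseline data, due to be complete before this version. The background section does not say which markers defined malnutrition; if they included laboratory values such as albumin, knowing SAF could not have moved those. The plan being replaced was a randomised trial of dietary AGE restriction, and nothing shows that raters expected a malnutrition link at baseline. The shifts illustrated here also fall well short of a strong correlation.

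A reader might also infer that the SAF operator scores SGA and vision. That is possible but not stated: responsibility for data collection is not the same as performing each rating, and other sections refer more widely to study staff and a delegation log.

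Three further points stand. Study 2's primary endpoint is change in SAF, so SGA rating does not affect its measurement. Vision is a side issue: it uses standard charts and plays no part in the nutrition association. And the planned analyses already relate SAF to laboratory and anthropometric markers, so a signal confined to SGA could be noticed if the results were shown together.

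As a caveat, the body headings on randomization and blinding have no visible text and the schematics are not shown, so a statement on masking may be absent from the available text. The synopsis row and the assessment sections contain none.

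What remains is that nothing written prevents the remaining SGA scores from being given with SAF known.

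**Conclusion.** The point holds as an inexpensive improvement, limited to SGA-based secondary results at the remaining Study 1 follow-up visits and at baseline and month 6 of Study 2. Rater, order and masking are unspecified, and the team that collects the data includes the SAF operator and has already acted on the hypothesis. Under the assumed shifts in 10% to 30% of ratings, the false-positive rate at n = 140 rises from 5% to about 7-28% (high-SAF half only) or 15-73% (two-way), with mean two-way correlations of only about −0.08 to −0.21. The shift shares and the SGA distribution are assumptions; the documents support no particular value, and the true bias may be nil. The point is no evidence that the baseline association is false.

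**What to change.** In the data collection sections of Study 1 and Study 2, add: *At visits with both assessments, SGA (and, where feasible, the pre-dialysis vision tests) is scored and entered on the CRF before that day's SAF reading and without consulting earlier SAF values. SAF is recorded on a separate CRF page. The rater and the order of assessments are recorded.*

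In the Statistics section, state that the SAF association with SGA will be reported beside those with the laboratory and anthropometric markers.

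Reconcile the two statements of SAF timing in HD participants so that the order can be applied.

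**Cost.** A fixed order within existing visits, one extra CRF page and two extra fields; no additional assessor. Scheduling around dialysis becomes slightly less flexible. Masking stays partial, because raters may recall earlier SAF values and post-dialysis vision tests will follow the SAF reading when both fall on the same day. The change cannot alter scores already recorded.
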